Pentoxifylline (PTX), a methylxanthine-derivative and nonspecific phosphodiesterase inhibitor with combined anti-inflammatory and antifibrogenic properties ⁽¹⁴⁾, can lower the levels of circulating proinflammatory cytokines, such as TNF- α , IL-1 β and IL-6, by means of a cyclic adenosine monophosphate (cAMP)-dependent mechanism ⁽¹⁵⁾. Furthermore, pentoxifylline has been proposed to have antioxidant properties ⁽¹⁵⁾. Moreover, pentoxifylline facilitates synthesis and release of serotonin and inhibits its uptake, suggesting that pentoxifylline enhances serotonergic presynaptic response in the CNS ⁽¹⁶⁾. In addition, it showed antidepressive-like effects in a rat model of acute myocardial infarction ⁽¹⁷⁾.

Aim of the study

The aim of the current study is to evaluate the potential antidepressant effect of pentoxifylline in adult patients with MDD. We hypothesized that MDD patients taking pentoxifylline as adjuvant would present greater amelioration of their depressive symptoms than patients taking placebo. Furthermore, we will assess the relationship between HAM-D score and several peripheral biomarkers as well as their role in diagnosis and therapeutic targets of MDD.

Patients and methods

Eighty adult outpatients who will meet the diagnostic and statistical manual of mental disorder IV (DSM-IV) criteria for major depression will be participated in the trial ⁽¹⁸⁾. Patients will be recruited from the armed psychiatry hospital, Egypt. Patients have a baseline Hamilton Rating Scale for Depression (Ham-D) score of at least 18 ⁽¹⁹⁾. Patients will be allocated in a random fashion: 40 patients will receive escitalopram 20 mg/day plus placebo (Control group) and 40 patients will receive escitalopram 20 mg/day plus pentoxifylline 800 mg/day (400mg bid) (morning and evening). Treatment duration will be 12 weeks. Adherence to the study medication will be assessed by collecting the empty blister packs of the consumed drugs from the patients every 4 weeks. Patients will be assessed by a psychiatrist at baseline, 4, 8, and 12 weeks after starting the medication. Any unexpected risks appeared during the course of the research will be cleared to participants and the ethical committee on time. An informed consent will be obtained from all participants in this research.

Measurements:

1. Full patient history, demographic data and clinical examination.
2. Patients will be assessed by a psychiatrist at baseline, 4, 8, and 12 weeks after starting the medication. The principal measure of the outcome will be the 17-item Ham-D. Remission is defined as an endpoint Ham-D total score ≤ 7 . Treatment response is defined as at least 50% improvement during the study period in the Ham-D scale. The mean decrease in Ham-D score from baseline will be the main outcome measure of response of depression to treatment (Primary outcome).
3. Questionnaire to evaluate the side effects of the study medications.
4. **Biological markers (Secondary outcome):** Blood sample collection at baseline and after the treatment to evaluate the following:
 - i) Serum level of Brain-derived Neurotrophic Factor (BDNF)
 - ii) Serum Serotonin level
 - iii) Serum levels of the following proinflammatory and anti-inflammatory markers:
 - Tumor necrosis factor-alpha (TNF-a)

- Interlukin-6 (IL-6)
 - Interlukin-10 (IL-10)
- iv) Serum levels of 8-hydroxy-2'-deoxyguanosine (8-OHdG), a biomarker of oxidative damage.

Inclusion criteria:

- 1- Eighty adult outpatients with the Diagnostic and Statistical Manual of Mental Disorders-IV (DSM-IV) diagnosis of MDD based on a MINI Neuropsychiatric Interview (MINI) (American Psychiatric Association., 2000; Sheehan et al., 1998), without psychotic features and a total 17 item HAM-D score of at least 18 with item 1 (depressed mood) scored 2 or greater were eligible.
- 2- Patients were requested to be free of all the psychotropic and anti-inflammatory medications for at least 4 weeks before participating in the study.

Exclusion criteria:

1. Patients with bipolar I or bipolar II disorder
2. Patients with personality disorders
3. Patients with eating disorders
4. Patients with substance dependence or abuse
5. Patients with concurrent active medical condition
6. Patients with history of seizures
7. Patients with history of receiving Electroconvulsive therapy (ECT)
8. Patients with inflammatory disorders
9. Patients with allergy or contraindications to the used medications
10. Patients with finally pregnant or lactating females

Statistical analysis:

All tests of treatment effect will be conducted by external statistician blind to group allocation, at a two-sided significance level of 0.05, and no adjustments were made for multiple comparisons. Type III sums of squares will be used to adjust for unbalanced data in the interactions of these models of variance. Importantly, general linear model for analysis of covariance (ANCOVA) model will be used for the primary analysis of change from baseline to endpoint in HAM-D total score. The primary analysis was performed using a mixed-effects model repeated measures (MMRM) ANCOVA. As a sensitivity analysis, will be carried out using the last observation carried forward (LOCF) approach in case of dropouts. Furthermore, a two-way repeated measures analysis of variance (ANOVA) for HAM-D score (time–treatment interaction) will be used. The two groups as a between-subjects factor (group) and the four time interval measurements during treatment as the within-subjects factor (time) will be

considered. Moreover, repeated measures ANOVA will be used to test the time x group interaction on the changes in the biomarkers between baseline and week 12 in the two groups. Chi square test was used for the qualitative variables. The statistical analysis was performed with IBM©SPSS® Statistics V 22. Pearson's correlation will be calculated to assess the relationship among variables.

References:

- 4- **Capuron L and Miller AH.** Immune system to brain signaling: neuropsychopharmacological implications. *Pharmacology & Therapeutics*. 2011; 130(2):226-38.

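### Minor: response and remission have no named analysis, and the only test that fits them uses neither baseline HAM-D nor the earlier scores of patients without a week-12 score

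*Combined protocol and SAP*

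**What the plan says.** Measurements, item 2, makes the mean HAM-D decrease the primary outcome and defines two binary outcomes beside it. For response: "Treatment response is defined as at least 50% improvement during the study period in the Ham-D scale". For remission, with a cut-off of 7 or less: "Remission is defined as an endpoint Ham-D total score". Neither definition names a visit, and neither outcome is ranked; the outcomes labelled secondary are the biomarkers.

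Patients and methods states "Treatment duration will be 12 weeks", with assessments at baseline and weeks 4, 8 and 12.

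The Statistical analysis section covers the HAM-D total in detail: "The primary analysis was performed using a mixed-effects model repeated measures (MMRM) ANCOVA". For categorical data it has one line: "Chi square test was used for the qualitative variables". Dropout appears once, as a sensitivity analysis "carried out using the last observation carried forward (LOCF) approach in case of dropouts", in a sentence without a subject that directly follows the primary model. For the biomarkers the section does name the visit: "changes in the biomarkers between baseline and week 12 in the two groups".

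**The concern.** A two-by-two chi-square on observed week-12 status has no place for a covariate and no place for a patient whose week-12 score is missing. The primary model keeps such a patient through the week-4 and week-8 scores, so the same trial would treat the same dropout in two ways. Baseline HAM-D, collected in everyone, would also go unused in the test.

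The main stake is precision. Some bias is added if dropout depends on earlier scores and differs between arms. The classification of a missing score is also left open, and it can change a borderline result. Suppose 6 patients per arm are missing and responders are 24/34 on active and 16/34 on control. The uncorrected chi-square on complete cases is 68 × (24×18 − 10×16)² / (34×34×40×28) = 3.89, p = 0.049. Counting the missing as non-responders gives 24/40 and 16/40, so 80 × (24×24 − 16×16)² / (40×40×40×40) = 3.20, p = 0.074.

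**Working it through.** The plan has no power, rate, SD, correlation or dropout figure, so there is nothing of its own to reproduce.

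**From the documents:** 40 per arm, two-sided 0.05, visits at baseline and weeks 4, 8 and 12, cut-offs of 50% improvement and 7 or less.

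**Assumed:** HAM-D rounded and limited to 0–52. Baseline normal with mean 24 and SD 3, truncated at 18 or more. SDs 5, 6 and 6.5 at weeks 4, 8 and 12. Post-baseline correlation 0.7 between adjacent visits and 0.49 between weeks 4 and 12. Baseline correlation r = 0.1, 0.3 or 0.5 with each later visit. Means at weeks 0/4/8/12: control 24/18/14/11, active 24/17/12/7.5. At r = 0.3 this gives week-12 response 58% vs 78% and remission 29% vs 50%. Half the dropout falls after week 4 and half after week 8, with odds doubling per SD of the last seen score.

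**Methods compared:**
- Complete-case Pearson chi-square.
- Multiple imputation with M = 20, within arm: week 8 from baseline and week 4, then week 12 from all earlier scores; then logistic regression on treatment and baseline x. The standardised risk difference is (1/N) Σ [expit(b0 + b1 + b2·xᵢ) − expit(b0 + b2·xᵢ)], with delta-method variance, pooled as T = W + (1 + 1/M)B.

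**Step 1, no missing scores.** Power change from baseline adjustment alone, at matched type I error (20,000 trials per cell; a smaller effect was also run). Response: −0.8 to +1.5 points throughout. Remission: −0.7 to −0.4 at r = 0.1, +0.6 to +1.1 at 0.3, +3.0 to +5.2 at 0.5.

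**Step 2, 20% dropout in each arm** (4,000 trials per cell, noise about 1 point). Power, complete-case chi-square to proposed method:

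| r | Response | Remission |
|---|---|---|
| 0.1 | 37 to 41% | 40 to 42% |
| 0.3 | 40 to 43% | 41 to 44% |
| 0.5 | 43 to 47% | 42 to 49% |

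The gains are 2 to 7 points. With 10% dropout per arm at r = 0.3, both outcomes go from 45 to 47%. At r = 0.3 and 20% dropout, the sampling SD of the difference falls from 12.3 to 10.8 points for remission (variance ratio (10.8/12.3)² = 0.77) and from 11.3 to 10.8 for response ((10.8/11.3)² = 0.91). Over steps 2 and 3, type I error was 4.2–5.6% for the proposed method and 4.4–6.0% for the chi-square.

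**Step 3, unequal dropout, r = 0.3.** Complete-case difference against the true one, in points:

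| Dropout, control/active | Response | Remission |
|---|---|---|
| 10%/20% | 20.7 vs 19.8 (+0.9) | 22.5 vs 20.7 (+1.8) |
| 20%/10% | 17.9 vs 19.6 (−1.7) | 19.6 vs 20.7 (−1.1) |

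In the first row the proposed method has 1 to 2 points less nominal power, because the complete-case difference is inflated. In the second, power rises from 37 to 44% (response) and from 37 to 46% (remission).

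**Step 4, LOCF, r = 0.3.** Response is 17.0 against 20.1 with 20% dropout per arm (−3.1), and 13.4 against 19.8 with 10%/20% (−6.4). Over the cases examined the error was about 0 to 7 points, smallest for remission with heavier dropout on control.

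**Step 5, dropout depending on the unseen week-12 score, r = 0.3.** Differences in points:

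| Outcome, dropout control/active | True | Imputed | Complete cases |
|---|---|---|---|
| Response, 10%/20% | 19.7 | 21.9 | 21.9 |
| Response, 20%/10% | 19.8 | 18.0 | 16.9 |
| Remission, 10%/20% | 20.3 | 22.4 | 23.9 |
| Remission, 20%/10% | 20.5 | 19.8 | 19.1 |

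**Step 6, visit.** Response is 58% vs 78% at week 12 (20 points) and 64% vs 81% at any visit (17 points). The standard error is √(0.58×0.42/40 + 0.78×0.22/40) = 0.102, or about 10 points, so this 3-point shift is small.

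**The case against.** The strongest reply is that the plan never assigns the chi-square to response or remission and never says that patients are dropped. The categorical variables in question could be demographics or side effects, and LOCF is the only dropout method named. A reader might infer a rule that excludes patients without a week-12 score, and the documents do not support that. Exclusion is only what a chi-square on observed scores does by default, and the link to these outcomes is itself an inference. It stands that no other method in the plan fits them and that no main-analysis rule for a missing score is given. Reading LOCF more widely does not close the gap, because step 4 shows it further from the truth than complete cases in those scenarios.

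A reader might also infer that response may be reached at any visit. That reading is strained: treatment and the last visit both end at week 12, which is the natural reading of both definitions. Naming the visit is a clarification.

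It is fair, too, that the biases of 1 to 2 points are small against sampling SDs of 11 to 12, that the gain for response with complete data is negligible, and that steps 2 and 3 are missing at random by construction. They show only what imputation does when its assumption holds. These points limit the importance of the concern but do not remove it.

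**Conclusion.** The point holds as a minor one. The better analysis uses data already collected and rests on the missing-at-random assumption that the planned primary model already makes. Its benefit is about 2 to 7 points of power with 20% dropout per arm, about 2 points with 10%, and protection against a 1 to 2 point error when dropout differs by arm and depends on earlier scores. If dropout depends on unseen scores, imputation is off too, though complete cases were off by the same or more. Every size depends on assumed means, SDs, correlations and dropout.

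It would go too far to call the chi-square invalid or to say that the trial's main conclusion is at risk. The test is valid, the primary outcome is analysed separately, the two binary outcomes are unranked, and the plan says "All tests of treatment effect will be conducted by external statistician blind to group allocation". Blinding limits selective choice of a rule but does not supply the rule.

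**What to change.** In the Statistical analysis section, before unblinding:

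- Judge both outcomes at week 12: response as at least a 50% reduction from baseline in the 17-item HAM-D, remission as a total of 7 or less.
- Analyse all randomised patients. Multiply impute a missing week-12 total within arm from baseline, week 4 and week 8, then apply the cut-offs.
- Fit logistic regression on treatment and baseline HAM-D. Base inference on the pooled standardised risk difference with its 95% CI, and report the adjusted odds ratio beside it. The pooled Wald test of the odds ratio should not carry the inference: with 20 imputations its type I error was 3.0–4.1%, and its power ran from 7 points below to 1 point above the complete-case chi-square.
- Keep the chi-square as descriptive.
- If a sensitivity analysis counts missing as failure, state that it can move the difference substantially in either direction when dropout differs by arm. At r = 0.3, response was 10.8 against a true 19.8 with 10% control and 20% active dropout, and 22.2 against 19.8 with the rates reversed.

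The cost is SAP wording, one imputation step and one model, with no new visits or data. It was not checked whether the SPSS version named in the plan gives the pooled standardised risk difference directly. There is no gain, and up to about 1 point of power may be lost, if no scores are missing and the baseline correlation is low. Nominal power is 1 to 2 points lower if dropout is heavier on active.

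### LOCF is the only sensitivity analysis planned for dropout: it applies one fixed assumption, and missing-at-random is not varied over any stated range

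*Combined protocol and SAP*

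**What the plan says.** The combined protocol and SAP describes its HAM-D analyses in one paragraph under Statistical analysis. Dropout is addressed once: "As a sensitivity analysis, will be carried out using the last observation carried forward (LOCF) approach in case of dropouts".

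The same paragraph calls two analyses primary. The first is an endpoint ANCOVA fitted as a general linear model, of which the text says that this "model will be used for the primary analysis of change from baseline to endpoint in HAM-D total score". A second sentence reads: "The primary analysis was performed using a mixed-effects model repeated measures (MMRM) ANCOVA". It then adds "a two-way repeated measures analysis of variance (ANOVA) for HAM-D score", which is not labelled a sensitivity analysis and has no missing-data rule.

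Nothing else in the document deals with missing HAM-D scores. It contains no multiple imputation, reference-based or delta-adjusted imputation, pattern-mixture model or tipping point. It gives no expected dropout rate and does not state MAR; the choice of an MMRM implies it.

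On the design, Patients and methods says "40 patients will receive escitalopram 20 mg/day plus placebo (Control group) and 40 patients will receive escitalopram 20 mg/day plus pentoxifylline 800 mg/day", and "Patients will be assessed by a psychiatrist at baseline, 4, 8, and 12 weeks after starting the medication".

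**The concern.** An MMRM gives a valid week-12 difference if data are missing at random given the scores already observed. The observed data cannot test that. The useful step is to depart from MAR by stated amounts and see whether the conclusion changes. LOCF does not do this, for two reasons.

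- **It fixes one assumption.** Every patient who leaves keeps the last score. Patients enter with HAM-D of at least 18 after at least 4 weeks without psychotropic drugs, start escitalopram in both arms, and are judged on how far the score falls. A frozen score, possibly the baseline score, is a weak choice as the only alternative. Calling it implausible is a judgement, since the plan gives no HAM-D course, but a reasonable one.
- **Its size and direction are not chosen.** They follow from how many patients leave each arm and when. The same rule can be harsh on pentoxifylline, mild, or favourable to it.

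At stake is the support for the main conclusion: the reader would not learn how far it depends on MAR.

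**Working it through.** **From the plan:** 40 patients per arm; visits at baseline and weeks 4, 8 and 12; two-sided 0.05. The plan gives no effect size, SD or dropout rate, so there is no figure of its own to reproduce.

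**Assumed for illustration:** control means 24/19/16/14 and pentoxifylline means 24/18/14/11 at the four visits (true week-12 difference 11 - 14 = -3); dropout unrelated to outcome, so MAR holds. Timing A spreads losses evenly after baseline, week 4 and week 8. Timing B has losses only after weeks 4 and 8, so that no baseline score is carried forward; the plan does not say whether patients without a post-baseline score enter the LOCF analysis.

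**Step 1, formula.** Let d be the dropout share in an arm and R the mean improvement still to come at the last visit attended. LOCF raises that arm's mean final score by d x R, so

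LOCF difference = true difference + (dP x RP - dC x RC).

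- Timing A: RC = (10 + 5 + 2)/3 = 5.67; RP = (13 + 7 + 3)/3 = 7.67.
- Timing B: RC = (5 + 2)/2 = 3.5; RP = (7 + 3)/2 = 5.0.

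Example, 10%/30%, timing A: 0.30 x 7.67 - 0.10 x 5.67 = 1.73, so the estimate is -3 + 1.73 = -1.27.

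**Step 2, results.** Dividing the shift by dP gives the single delta, added to pentoxifylline dropouts only, to which LOCF is equivalent.

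| Dropout, control/pentoxifylline | LOCF estimate, A | LOCF estimate, B | Equivalent delta, A | Equivalent delta, B |
|---|---|---|---|---|
| 10%/10% | -2.80 | -2.85 | +2.0 | +1.5 |
| 20%/20% | -2.60 | -2.70 | +2.0 | +1.5 |
| 10%/20% | -2.03 | -2.35 | +4.8 | +3.3 |
| 10%/30% | -1.27 | -1.85 | +5.8 | +3.8 |
| 20%/10% | -3.37 | -3.20 | -3.7 | -2.0 |
| 30%/10% | -3.93 | -3.55 | -9.3 | -5.5 |

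A negative delta favours pentoxifylline. The sign changes when dC/dP passes RP/RC: 7.67/5.67 = 1.35 (A) or 5.0/3.5 = 1.43 (B).

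**Step 3, the MMRM on the same data.** In simulations with these means (20,000 trials per pattern; SDs 3.5/4.5/5/5.5; correlation 0.7 between adjacent visits), the MMRM averaged -2.99 to -3.01 at 20%/20% and at the four unbalanced patterns. The shifts belong to LOCF alone.

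**Step 4, other assumed means.** With mean changes at weeks 4/8/12 of -6/-9.5/-12 (control) and -7/-11.5/-15 (pentoxifylline) and a constant dropout hazard per interval, the LOCF estimate is -2.80 at 10%/10%, -2.59 at 20%/20%, -0.91 at 10%/30% and -4.27 at 30%/10%. The pattern is the same.

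**Step 5, what a chosen delta shows.** The difference moves by dP x delta. With an MAR estimate of -3, a common SD and the SE held at SD x sqrt(2/40), significance is lost at delta = (3 - 1.96 x SE)/dP.

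- SD 5: SE 1.12, and 1.96 x SE = 2.19. The tipping delta is 8.1, 4.0 or 2.7 points at 10%, 20% or 30% pentoxifylline dropout.
- SD 6: SE 1.34, and 1.96 x SE = 2.63. The tipping delta is 3.7, 1.9 or 1.2 points.

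A clinician can judge whether such a delta is credible. LOCF gives no such number.

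**The case against.** The strongest reply is that LOCF is itself a departure from MAR, that with low and balanced dropout it changes little (-2.80 against -3 at 10%/10%), and that the plan gives it no decision role. All of this stands. It limits the weight of the point but does not remove it: a single departure whose direction depends on the dropout pattern is not a range.

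A reader might go further and infer any of three things that do not hold.

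- *LOCF is discredited because it often overturns a significant MMRM when MAR is true.* Under the assumptions above (timing A), it does so in 27.5% of MMRM-significant trials at 20%/20% and 74.7% at 10%/30%. But deltas of 1, 3 and 6 do so in about 10%, 28% and 55% at 20%/20%, and about 15%, 42% and 75% at 10%/30%. Any unfavourable departure has this effect, so it does not separate LOCF from the remedy.
- *The trial's type I error is inflated.* LOCF can reject too often under unbalanced dropout, but that is the error of a supportive analysis. No sentence makes the conclusion depend on LOCF agreeing with the primary result.
- *The primary estimate is biased.* LOCF is named only as the sensitivity analysis, and an MMRM does not use carried-forward scores.

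Delta adjustment is also not the only acceptable choice: control-based imputation would be reasonable too. What matters is that the departure is explicit and prespecified.

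**Conclusion.** The point holds as a cheap improvement to the plan, not as a flaw in the primary result. The only planned dropout check applies one fixed assumption. Under the assumed means, its effect ranges from 0.15 to 0.20 points toward zero at 10%/10% dropout, through 1.15 to 1.73 points toward zero at 10%/30%, to 0.55 to 0.93 points in favour of pentoxifylline at 30%/10%.

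These sizes rest on assumed HAM-D means, dropout shares and timing, and on dropout unrelated to outcome. If dropout proves low and balanced, little is lost in practice. The finding about the plan itself needs none of these assumptions: it sets no range over which MAR is varied. Applying the point to the primary result does presume that the MMRM is the primary analysis, which the document leaves unsettled.

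**What to change.** In the Statistical analysis section:

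1. State that the MMRM assumes MAR.
2. Replace LOCF as the sensitivity analysis; keep it at most as a descriptive supplement.
3. Specify multiple imputation of missing HAM-D under MAR, within arm, from baseline and earlier visits. Follow it with a delta-adjusted (tipping-point) analysis that adds delta to imputed pentoxifylline-arm values, over a range that the sponsor prespecifies and justifies. A range of 1 to 6 points would be one example only.
4. Report the estimate and 95% CI at each delta and, if the primary result is significant, the delta at which significance is lost.
5. Tabulate dropout by arm and last visit attended, and by reason only if reasons are recorded. The document describes no such recording, and the fix does not depend on it.

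The two sentences naming different primary analyses are a separate issue and must be reconciled, so that it is clear which analysis this one supports.

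The cost is SAP wording and modest programming on HAM-D scores already to be collected, with no extra visits or patients. The downsides are that delta-adjusted imputation may need syntax or a package beyond the menus of the named SPSS version, and that the delta range must be justified.

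### The six secondary biomarkers are tested without baseline adjustment; ANCOVA on the samples already planned would usually be more precise, at the cost of one degree of freedom per marker

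*Combined protocol and SAP*

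**What the plan says.** Measurements, item 4, is headed "Biological markers (Secondary outcome") and lists six serum markers: BDNF, serotonin, TNF-alpha, IL-6, IL-10 and 8-OHdG. Each is measured twice: "Blood sample collection at baseline and after the treatment to evaluate the following".

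The Statistical analysis section gives their test: "repeated measures ANOVA will be used to test the time x group interaction on the changes in the biomarkers between baseline and week 12". No covariate is named for them. ANCOVA appears only for the depression score: "ANCOVA) model will be used for the primary analysis of change from baseline to endpoint in HAM-D total score". Tests are run "at a two-sided significance level of 0.05, and no adjustments were made for multiple comparisons".

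Patients and methods states that allocation is random, with 40 patients in each of two arms and 12 weeks of treatment.

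**The concern.** A repeated-measures ANOVA with one pre-treatment and one post-treatment value looks like a longitudinal model, but its time-by-group test only compares mean change between arms. Subtracting the whole baseline value is the best use of it only if the true regression slope of week 12 on baseline is 1. If the slope is lower, as it is whenever the two SDs are equal and the correlation is below 1, subtraction over-corrects and adds noise.

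Two things are at stake. With 40 patients per arm, the intervals for all six markers may be wider, and the power lower, than the collected data allow. The planned estimate also moves with chance baseline differences between the arms. The markers matter to the trial: the Aim of the study includes them, and the rationale for pentoxifylline rests partly on lowering cytokines.

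**Working it through.** The plan has no biomarker power calculation, so there is no figure to reproduce.

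**Inputs from the documents.** Two samples per patient and six markers (Measurements, item 4); n = 40 per arm, N = 80, random allocation (Patients and methods); two-sided alpha 0.05 (Statistical analysis).

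**Assumptions.** The correlation rho between baseline and week 12, the SDs and the effect size are not given. Results are shown over ranges, for normal data and 40 completers per arm.

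**1. Identity.** In simulated data the interaction F equals the squared pooled t on change: with 40/40 patients, F = t² = 2.732 (p = 0.1024); with 36/31, F = t² = 0.2697 (p = 0.6053). The planned test therefore has 40 + 40 − 2 = 78 error df.

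**2. Variance, equal SDs.** Per patient, the change score has variance 2σ²(1 − rho) and ANCOVA has σ²(1 − rho²). The ratio is (1 − rho²)/[2(1 − rho)] = (1 + rho)/2. Estimating the slope multiplies the ANCOVA variance by about (N − 3)/(N − 4) = 77/76 = 1.013 and leaves 77 df.

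**3. Precision and power.** The standard error is √(variance × 2/40). For example, at rho = 0.3 the change score gives √(1.4 × 0.05) = 0.265 SD and ANCOVA gives √(0.91 × 1.013 × 0.05) = 0.215 SD. Power comes from the noncentral t. Each pair below is planned test, then ANCOVA.

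| rho | Variance ratio (with slope cost) | 95% CI half-width, SD | Power, 0.4 SD | Power, 0.5 SD | Power, 0.6 SD |
|---|---|---|---|---|---|
| 0.3 | 0.65 (0.66) | 0.53, 0.43 | 32%, 45% | 46%, 63% | 61%, 79% |
| 0.5 | 0.75 (0.76) | 0.45, 0.39 | 42%, 53% | 60%, 72% | 75%, 86% |
| 0.7 | 0.85 (0.86) | 0.34, 0.32 | 63%, 69% | 81%, 87% | 93%, 96% |
| 0.9 | 0.95 (0.96) | 0.20, 0.20 | 98%, 98% | 99.9%, 99.9% | 100%, 100% |

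Before the slope cost, ANCOVA would match the planned precision with 80 × ratio = 52, 60, 68 or 76 patients.

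Simulation (20,000 trials per setting) agreed for 0.5 SD: 46.1% and 63.2% at rho 0.3, 59.9% and 71.5% at 0.5, 81.6% and 87.0% at 0.7. Type I error was about 5% for both methods.

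**4. Break-even, equal SDs.** (1 + rho)/2 × 77/76 = 1 gives rho = 2 × 76/77 − 1 = 0.974. Above that, ANCOVA loses at most about 1.3% of variance.

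**5. Unequal SDs.** With k = week-12 SD / baseline SD, the ratio is k²(1 − rho²)/(1 + k² − 2 rho k). At rho 0.3, 0.5, 0.7 and 0.9 it is 0.50, 0.57, 0.63 and 0.61 for k = 0.8, and 0.78, 0.89, 0.98 and 0.95 for k = 1.25.

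**6. Chance imbalance.** The baseline difference between arms has standard error √(2/40) = 0.22 SD, so a difference of 0.3 SD or more in either direction arises in about 18% of trials for any one marker. With equal SDs, a 0.3 SD imbalance moves the change-score estimate by 0.3 × (1 − rho) = 0.21, 0.15, 0.09 or 0.03 SD at the four correlations. For ANCOVA the expected shift is about 0.

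**The case against.** The planned test is valid: it is unbiased under randomisation and keeps its type I error. The outcomes are secondary, and the plan sets no biomarker power target that it would miss. All of this stands, and it makes the point one of efficiency.

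The size of the gain is not fixed by the documents. It runs from almost nothing (equal SDs, rho 0.9) to large (38% to 60% power for 0.5 SD at rho 0.1), and the six markers need not share one correlation. This also stands, so no single row of the table is the expected gain. It does not favour the planned test, because ANCOVA adapts to the correlation and the change score does well only when the slope is near 1.

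ANCOVA's advantage is not absolute. It costs one df and about 1.3% of variance, a net loss when the true slope is 1. If completers are unequal between arms and the slopes differ by arm, a common-slope model has no strict guarantee of being more precise. These are narrow exceptions.

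Serum markers may be skewed, and the powers above then do not carry over. In log-normal data analysed on the raw scale, the gain for a 0.5 log-SD increase was smaller but remained (34% and 44% at rho 0.3; 58% and 61% at 0.7). In another log-normal simulation, with a reduction of 0.5 log-SD, it did not shrink (37% and 58% at log-SD 0.5, rho 0.3).

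**Conclusion.** The concern holds as an efficiency weakness in the secondary analyses. The planned biomarker test is a t-test on change and, apart from the exceptions noted, is no more precise than ANCOVA on the same two samples. With equal SDs the variance saved, before the slope cost, is 35%, 25%, 15% or 5% at rho 0.3, 0.5, 0.7 or 0.9. The gain is negligible near 0.9 only when the SDs are equal: with a week-12 SD 0.8 times baseline, the saving there is 39%. These sizes rest on assumed correlations, SDs and effects, normal data and 40 completers per arm. The direction rests only on the design: random allocation and a baseline value already collected. The change should be made, but nothing here invalidates the planned test.

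**What to change.** In the Statistical analysis section, replace the biomarker sentence with one stating that each marker's week-12 value will be analysed by ANCOVA with treatment as factor and that marker's own baseline value as covariate, reporting the adjusted between-group difference with its 95% confidence interval. Using change as the dependent variable with the same covariate gives the identical treatment estimate and standard error, so the plan's interest in change is kept. Within-group changes over time can still be reported descriptively.

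The cost is one sentence and one degree of freedom per marker. No patients, samples or visits are added, and the analysis runs in the SPSS package already named. Both methods use patients with both samples, so this change does not deal with missing week-12 samples, nor with multiplicity across the six markers.
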